**16.1.9 Documentation of Statistical Methods**

The final approved [Statistical Analysis Plan](#) for this study is provided in the following pages.

## 2 LIST OF ABBREVIATIONS AND DEFINITIONS OF TERMS

Abbreviation	Term
AE	adverse event
AED	antiepileptic drug
ATC	anatomical therapeutic class
BMI	Body Mass Index
BP	blood pressure
CI	confidence interval
CRF	case report form
C-SSRS	Columbia-Suicide Severity Rating Scale
ECG	electrocardiogram
EEG-IPS	electroencephalogram intermittent photic stimulation
EOT	end of treatment
LNH	low/normal/high
LS	least square
MedDRA	Medical Dictionary for Regulatory Activities
PD	pharmacodynamic(s)
PGx	pharmacogenomic
PK	pharmacokinetic(s)
PPR	photoparoxysmal response
PT	preferred term
SAE	serious adverse event
SAP	statistical analysis plan
SAS	Statistical Analysis System
SD	standard deviation
SI	Système International
SOC	system organ class
TEAE	treatment-emergent adverse event
TLG	tables, listings, and graphs
WHO DD	World Health Organization drug dictionary

### 3 INTRODUCTION

The purpose of this statistical analysis plan (SAP) is to describe the procedures and the statistical methods that will be used to analyze and report results for Eisai Protocol E2082-A001-201.

#### 3.1 Study Objectives

##### 3.1.1 Primary Objective

To assess pharmacodynamics (PD) activity of E2082 as measured by suppression of epileptic photoparoxysmal response (PPR) in the subject's most sensitive eye condition in the photosensitivity model as a proof of principle of efficacy in subjects with photosensitive epilepsy, compared to placebo

##### 3.1.2 Secondary Objectives

The secondary objectives of the study are:

- To assess the PD activity of E2082 as measured by suppression of PPR in each of the 3 eye conditions (eye closure, eyes closed, and eyes open), compared to placebo
- To assess PD activity of E2082 as measured by onset, maximum change, and duration of photosensitivity response in each of the 3 eye conditions (eye closure, eyes closed, and eyes open)
- To assess proportion of subjects with complete suppression, partial suppression, and no response of standardized photosensitivity response (SPR)
- To assess other central nervous system (CNS)-related effects of E2082 based on Bond-Lader Visual Analogue Scale (BL-VAS)
- To assess the safety and tolerability of E2082 following single oral dose administration
- To assess the pharmacokinetics (PK) of E2082 following single oral dose administration

##### 3.1.3 Exploratory Objective

To explore relationships between PK and PD.

#### 3.2 Overall Study Design and Plan

This is a multicenter, double blind, randomized, 6-sequence, 3-treatment, 3-period, crossover study with an Open-Label Treatment Period, in adult subjects with photosensitive epilepsy.

This study will have 2 phases: Pretreatment Phase and Treatment Phase.

The Pretreatment Phase will consist of a Screening Period (up to 3 weeks from Visit 1), during which each subject's study eligibility will be determined.

The Treatment Phase will consist of 3 blinded Treatment Periods for a randomized crossover design, followed by an Open-label Treatment Period. During the blinded Randomized Crossover Treatment Periods, there will be 3 Treatment Visits (Visit 2 [Treatment Period 1], Visit 3 [Treatment Period 2], and Visit 4 [Treatment Period 3]) evaluating single-dose administrations of either placebo, E2082 2.5 mg, or E2082 25 mg in a blinded manner. During the open-label treatment period, subjects will be administered a single dose of E2082 40 mg.

A recent protocol amendment ([Amendment 01; V2.0](#)) has modified the study design to allow for the evaluation of an open-label dose administration of E2082 10 mg in subjects as applicable, depending on the scenario the subject falls under and depending on the subject's response (photoparoxysmal response [PPR]) during blinded Treatment Periods, as described below.

**Scenario 1:** Newly enrolled or ongoing subjects who have completed up to the Treatment Period 3 at the time of Protocol Amendment 01 implementation, will undergo 1 treatment visit (Visit 5 [Treatment Period 4]) during the Open-label treatment period to receive a single-dose administration of E2082 40 mg or 10 mg; the dose to be administered will be provided by an independent unblinded biostatistician upon review of the subject's response data collected during Treatment Periods 1 through 3.

**Scenario 2:** Subjects who completed the open-label Treatment Period 4 (Visit 5), and have not completed the Follow-Up visit [Visit 6]) by the time of Protocol Amendment 01 implementation may continue the study as originally planned (ie, process to Follow-up Visit [Visit 6]) or may continue in the study to receive an additional open-label, single oral dose of E2082 10 mg in the Treatment Period 5 (Visit 8) before proceeding to Follow-up Visit (Visit 9).

**Scenario 3:** Subjects who completed the study (including Follow-Up visit [Visit 6]) before the implementation of Protocol Amendment 01 may be allowed to re-enter the study to receive an open-label, single-dose administration of E2082 10 mg after Screening 2 (Visit 7) dependent on the subject's response to treatment during the subject's initial study participation.

Treatment visits (i.e., Visit 2, Visit 3, Visit 4, and Visit 5) will each be separated by a 2-week ( $\pm 3$  days) washout interval for a total of approximately 6 weeks. Treatment Period 5 (Visit 8) will be 2 weeks ( $\pm 3$  days) after Treatment Period 4 (Visit 5) for subjects in Scenario 2, and after Screening 2 for subjects in Scenario 3. All subjects will undergo a Follow-up Period of 2 weeks ( $\pm 3$  days) after the last day of study product administration (Visit 5 and/or Visit 8, as applicable). (revised per Amendment 01).

[figure not shown]
Each subject will receive a single oral dose in a crossover sequence according to his/her randomization code for the treatment sequence in 3 double-blinded treatment periods.

**Table of Treatment Sequences**

Sequence	Double-Blind Treatment Periods		
	1 (V2)	2 (V3)	3 (V4)
1: ABC	Placebo	E2082 2.5 mg	E2082 25 mg
2: BCA	E2082 2.5 mg	E2082 25 mg	Placebo
3: CAB	E2082 25 mg	Placebo	E2082 2.5 mg
4: ACB	Placebo	E2082 25 mg	E2082 2.5 mg
5: BAC	E2082 2.5 mg	Placebo	E2082 25 mg
6: CBA	E2082 25 mg	E2082 2.5 mg	Placebo

A = Placebo; B = E2082 2.5 mg; C = E2082 25 mg;

An overview of the study design is presented by Figure 1 in the study protocol as follows.

ED = Early discontinuation, FU = Follow Up, Pd = period, R = randomization, Trt = treatment, WO = washout.

**Figure 1 : Design for a Crossover Study**

An overview of the changes related to amendment is described below in Figure 2.

Phase:	Pretreatment	Treatment	
Period:	Screening 2 (SCR-2)	Open-label Treatment  Trt Pd 5 (1 day)	Follow-Up 2 (FU-2)  FU Pd (14±3 days)
Visit:	7	8	9
Study Daya:	-21 to -1	1	15±3

FU = Follow-up, SCR = screening, Pd = Period

a: Study days are with respective to the day of Treatment Period 5 (Visit 8).

**Figure 2 : Study Design for Subjects in E2082-A001-201 - Scenario 3  
(Revised per Amendment 01)**

#### 4 DETERMINATION OF SAMPLE SIZE

Based on a similar study in subjects with photosensitive epilepsy (NCT02564029), an estimated standard deviation of the treatment group difference of the SPR in the subject’s most sensitive eye condition is 3.62. The width of a 90% CI of the mean group difference based on this standard deviation assumption and 6 subjects is 2.431. Therefore, a sample size of 6 would be sufficient to detect a mean group difference of 3 or larger with 90% confidence.

Approximately 9 subjects with photosensitive epilepsy and a stable PPR will be needed to be randomized in the study in order to obtain 6 evaluable subjects.

A subject will be defined as evaluable if the subject has completed at least 2 treatment periods (including one with placebo) and has more than 50% non-missing postdose PPR data in each period to get the average PPR value (i.e., at least 3 of 5 posedose PPR data are valid in each period).

Subjects who discontinue from the study early may be replaced after consultation with the sponsor.

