This photosensitivity range, defined as the difference between the highest and lowest flash rates that consistently elicit a PPR, can be used as a quantitative measure of photosensitivity and, therefore, epileptogenicity. In photosensitivity studies, a stable baseline is defined as the baseline at the Screening and Predose on the day of each Treatment Period. Usually during a photosensitivity study, the baseline is stable throughout the study. The photosensitivity range is measured repeatedly (up to 8 times) over the course of a single day, and the range can be measured rapidly (over a 5-minute interval) in an EEG laboratory. Reduction in the photosensitivity range can then be easily quantified after a single dose of an AED. This reduction has been used to demonstrate an antiepileptic effect for a number of AEDs currently marketed or in development, most notably valproate, levetiracetam, lamotrigine, brivaracetam, carisbamate, JZP4 (Jazz Pharmaceuticals), cenobamate (YKP3089, SK Life Sciences), and selurampanel (BGG492, Novartis). This POC model has been successful in identifying multiple drugs in early phase drug development that were subsequently effective in large clinical studies (Binnie, et al., 1986a; Binnie, et al., 1986b; Binnie, 1988; Kasteleijn-Nolst Trenité, et al., 1996; Kasteleijn-Nolst Trenité, et al., 2007; Trenité, et al., 2007; French and Krauss, 2014; Kasteleijn-Nolst Trenité, et al., 2015).

The intent of this study is to provide a POC signal and evidence of a dose-response relationship, and to inform the design and dose selection for Phase 2 of the clinical development program.

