#### Primary PD Analyses

The reduction in PPR response will be evaluated for 8 hours postdose during each Treatment Period. A diminution in response is anticipated with the dose range.

The primary endpoint, mean change from baseline of the average PPR in the most sensitive eye condition, will be summarized by treatment group, and analyzed using a mixed effects model for crossover part of the study. The mixed effects model for the crossover part of the study will include treatment (E2082 2.5 mg, 25 mg, and placebo), period, and sequence as fixed effects, baseline (predose) measurement as a covariate, and subject nested within sequence as a random effect. Least squares (LS) means, difference in LS means of each E2082 dose (2.5 mg or 25 mg) compared to placebo, and 90% CIs will be presented with no adjustments for multiplicity.

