## 13.2 SAS Code of Mixed Model for Primary PD Analyses

```
proc mixed data= xxx;
  class USUBJID TRTPN PERIOD SEQUENCE ;
  model AVAL = TRTPN PERIOD SEQUENCE BASE /SOLUTION ddfm= kr;
  random USUBJID(SEQUENCE) ;
  lsmeans TRTPN/alpha= 0.1 PDIFF CL
  pdiff=control('Placebo') ;
run;
```

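### The sample-size paragraph reports a normal-quantile half-width (2.431) as the width of the 90% CI; with t quantiles the full width is 5.6 to 6.0, and a true 3-unit difference is detected only a little more often than not

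*SAP*

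**What the plan says.** SAP section 4 takes the standard deviation of the treatment difference in SPR from an earlier study in the same condition ("most sensitive eye condition is 3.62") and plans about 9 randomised subjects, "needed to be randomized in the study in order to obtain 6 evaluable subjects". It then gives the precision, "The width of a 90% CI of the mean group difference based on this standard deviation assumption and 6 subjects is 2.431", and draws the conclusion: "Therefore, a sample size of 6 would be sufficient to detect a mean group difference of 3 or larger with 90% confidence". Protocol 9.7.2 and the synopsis carry the same sentences. No power, quantile or success rule is stated.

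SAP section 4 also defines who counts: "A subject will be defined as evaluable if the subject has completed at least 2 treatment periods (including one with placebo"), with at least 3 of the 5 postdose PPR values valid in each period. The protocol has no such definition.

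The primary analysis reports "Least squares (LS) means, difference in LS means of each E2082 dose (2.5 mg or 25 mg) compared to placebo, and 90% CIs", without multiplicity adjustment. The code in SAP 13.2 is "model AVAL = TRTPN PERIOD SEQUENCE BASE /SOLUTION ddfm= kr", with limits at alpha 0.1.

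**The concern.** There are three separate problems in two sentences.

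- **Label.** The number given as the width is a half-width.
- **Quantile.** It uses the normal quantile, whereas the planned analysis uses t quantiles on few degrees of freedom.
- **Inference.** The step from a half-width below 3 to being able to detect 3 is valid only if 3 is the observed difference. A reader can easily take it as a statement about a true difference of 3, which would need a power figure that the documents do not give.

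This is the only justification of the sample size in either document. Protocol 7.2.1 says "The intent of this study is to provide a POC signal and evidence of a dose-response relationship", and that the study should inform dose selection. Someone relying on section 4 would expect an interval less than half as wide as the one the trial is likely to produce. They could also read a CI that spans 0 as evidence against a 3-unit effect, although such a result is nearly as likely as not when a 3-unit effect exists.

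**Working it through.** **Inputs.** SD of the difference 3.62, n = 6 and target difference 3 (SAP 4); two-sided 90% CI, Kenward-Roger df, and a model with treatment, period, sequence, baseline and random subject (SAP 5.5.2 and 13.2); 6 sequences, 3 periods (SAP 3.2).

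**Reproducing the plan's figure.**

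SE = 3.62/√6 = 1.478. 
z half-width = 1.645 × 1.478 = **2.431**, matching the plan to three decimals. 
z full width = 2 × 2.431 = 4.86.

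**Degrees of freedom.** Six complete subjects give 18 observations. The subject/sequence, period, treatment and baseline terms take 6 + 2 + 2 + 1 = 11, leaving 7. A simple paired analysis has 6 − 1 = 5. Kenward-Roger may give a somewhat different value, so 7 and 5 serve as a working range.

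**Half-width = quantile × SE; power from the noncentral t with ncp = 3/1.478 = 2.03.**

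| Basis | Quantile | Half-width | Full width | CI at observed 3 | P(CI excludes 0), true 3 | True difference for 80% power |
|---|---|---|---|---|---|---|
| z | 1.645 | 2.431 | 4.86 | 0.57 to 5.43 | 65% | 3.7 |
| t, 7 df | 1.895 | 2.800 | 5.60 | 0.20 to 5.80 | 57% | 4.09 |
| t, 5 df | 2.015 | 2.978 | 5.96 | 0.02 to 5.98 | 54% | 4.29 |

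The t-based full width is 5.60/2.431 = 2.3 to 5.96/2.431 = 2.5 times the stated width. Of that, a factor of 2 is the label; the quantile adds 15% (1.895/1.645) to 22% (2.015/1.645).

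**Sensitivity to the SD.** The baseline-adjusted SD is not given. Assuming 3.0 to 4.0 at 7 df, the half-width runs from 2.32 to 3.09 and the chance at a true 3 from 71% to 50%.

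**Sensitivity to the pair count.** Take 6 evaluable subjects, one per sequence, with one of them lacking the dose in question (17 observations, 6 df, no SE change from baseline assumed). The SE becomes 1.610 and the half-width 1.943 × 1.610 = 3.13, whichever sequence loses the period. An observed difference of 3 then no longer excludes 0, and the chance at a true 3 is 50%.

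**If all 9 randomised subjects are complete.** SE = 3.62/√9 = 1.207. The chance at a true 3 is 73% (8 df, paired) or 76% (13 df, model: 27 − 14).

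**The case against.** The best defence is that the conclusion survives. The text speaks of 90% confidence, not 90% power. With 6 complete pairs, an observed difference of 3 gives a CI above 0 at both 7 and 5 df. The study is a proof of principle reported with descriptive CIs, so asking for power answers a claim the plan does not make. This stands in part: the error does not invalidate N = 6. It does not rescue the stated width, which is wrong under any quantile, and the wording about detection still invites the power reading.

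A second objection is that 54% to 57% is the floor. About 9 subjects are randomised, early dropouts may be replaced, and the primary model uses the whole PD Analysis Set. That is fair: with complete data the chance at a true 3 is 62% to 65% for 7 subjects and 68% to 71% for 8, before the 73% to 76% for 9. But the plan rests its own case on 6.

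Third, the 7-df figures are illustrative. They assume balanced sequences and no SE cost from the baseline covariate; a simulated uninformative baseline gives a median SE of about 1.52, and a predictive one could lower it. This is right, and is why the figures should be given as a range with their assumptions.

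Lastly, the pair count could be called a separate matter. It belongs here because the same section defines evaluability and uses 6 as the divisor.

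**Conclusion.** The concern holds. The 2.431 in SAP 4, Protocol 9.7.2 and the synopsis is a normal-quantile half-width labelled as a width. For the planned t-based analysis with 6 pairs, the half-width is about 2.8 to 3.0 and the full width 5.6 to 6.0. The claim about detecting 3 is correct only for an observed difference, and with as little as 0.02 to spare; for a true difference of 3 the chance is 57% to 54%.

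These figures take 3.62 at face value as the SD of within-subject differences (its source could not be checked), assume the same SD after baseline adjustment, and need 6 placebo-dose pairs per contrast. The point should be fixed, but it is an error of statement and interpretation and does not undermine the design.

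**What to change.** Keep N, the evaluable definition and the analysis. Replace the two sentences in SAP 4, Protocol 9.7.2 and the synopsis with:

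> With 6 subjects contributing to a dose-placebo difference and an assumed SD of the difference of 3.62, the half-width of the two-sided 90% CI is about 2.8 (7 df, planned model, assuming the same SD after baseline adjustment) to 3.0 (5 df, paired), a full width of 5.6 to 6.0. A true difference of 3 has about a 57% (7 df) to 54% (5 df) chance of giving a CI that excludes 0; 80% power needs a true difference of about 4.1 to 4.3. These figures assume 6 placebo-dose pairs for the contrast, which the evaluable definition in SAP section 4 does not guarantee.

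The protocol text should point to SAP 4 for that definition, since it has none of its own. A sentence giving 73% to 76% if all 9 subjects are complete could be added for balance. In the primary PD table, print the number of placebo-dose pairs beside each CI.

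The cost is wording in three places and one count per contrast. The protocol part needs a sponsor-approved amendment or administrative change under Protocol 11.1. The stated precision becomes less favourable; nothing in the conduct or analysis changes.

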## 5 STATISTICAL METHODS

All descriptive statistics for continuous variables will be reported using mean, standard deviation (SD), median, minimum and maximum unless otherwise specified. Categorical variables will be summarized as number (percentage) of subjects.

Study data will be unblinded once double-blind treatment period has completed. Two sets of analyses tables will be created: one set after the unblinding using all the available data until that point and another set after all the subjects have completed the last study visit.

### 5.1 Study Endpoints

#### 5.1.1 Primary Endpoint

The primary endpoint is mean change from baseline in the PPR range in each subject's most sensitive eye condition at each dose level of E2082 as compared to placebo.

#### 5.1.2 Secondary Endpoints

- Mean change from baseline in the PPR range in each of the 3 eye conditions (eye closure, eyes closed, and eyes open) at each dose level of E2082 compared to placebo
- Onset, maximum change, and duration of response in each of the 3 eye conditions (eye closure, eyes closed, and eyes open) at each dose level of E2082
- Frequency and percentage of subjects with complete suppression, partial response, and no response of SPR at each dose level of E2082
- Changes from baseline in BL-VAS at each dose level of E2082
- Incidence of TEAEs at each dose level of E2082
- Clinically significant changes from baseline in vital signs, serum chemistries, complete blood counts, or liver function tests after single doses of E2082, compared to placebo
- PK parameters of E2082 ( $C_{max}$ ,  $t_{max}$ , area under concentration-time curve from time 0 to 8 hours postdose [ $AUC_{(0-8h)}$ ])
- Relationship between PK parameters of E2082 onset, maximum change, and duration of impact on photosensitivity

### 5.2 Study Subjects

#### 5.2.1 Definitions of Analysis Sets

The Safety Analysis Set is the group of subjects who receive at least 1 dose of study drug and have at least 1 postdose safety assessment.

The Pharmacokinetic Analysis Set is the group of randomized subjects who receive at least 1 dose of study drug and have sufficient PK data to derive at least 1 PK parameter.

The Pharmacodynamic Analysis Set is the group of randomized subjects who receive at least 1 dose of study drug and have sufficient PD data to derive at least 1 PD parameter.

### 5.2.2 Subject Disposition

Number of subjects screened and screening failures (overall and by reason for failure) will be summarized. The number of subjects randomized along with the number of subjects received each dose of E2082 will also be presented.

Subjects who prematurely terminate their participation in the study will be summarized by the primary reason as well as any other reasons(s) for discontinuation from the study.

### 5.2.3 Protocol Deviations

Major protocol deviations will be presented as a listing.

### 5.2.4 Demographic and Other Baseline Characteristics

Demographic and other baseline characteristics for the Safety Analysis Set will be summarized overall using descriptive statistics by treatment groups and overall. Continuous demographic and baseline variables include age, height, and weight; categorical variables include sex, age group, race, and ethnicity.

### 5.2.5 Prior and Concomitant Therapy

Number (percentage) of subjects who took prior and concomitant medications, will be summarized by Anatomical Therapeutic Chemical (ATC) class and World Health Organization Drug Dictionary preferred term (PT).

Prior medications will be defined as medications that stopped before the dose of study drug in treatment period 1. Concomitant medications for a treatment group will be defined as medications that started after the date of the dose of study drug up to 28 days after the subject's dose or the next dose date in next treatment period, whichever is earlier.

Prior medications will be summarized overall and concomitant medications will be summarized by treatment group. The latest version before database lock will be used for analysis.

### 5.2.6 Treatment Compliance

Not Applicable.

## 5.3 Data Analysis General Considerations

Because of the crossover design of the study, analyses results will be presented by treatment

sequence (Sequence 1 to Sequence 6) and by treatment group (Placebo, E2082 2.5 mg, E2082 25 mg) as appropriate. For by treatment group summaries, data from subjects receiving a given treatment will be combined across various sequences.

For listings or data summaries where change from baseline measurements will be calculated and presented, unless stated otherwise, the last observed measurement, including unscheduled assessments, prior to the first dose of study drug in the first period will be considered the baseline measurement for all assessments except PPR related endpoints.

All descriptive statistics for continuous variables will be reported using number of observations (n), mean, standard deviation (SD), median, minimum, and maximum unless otherwise specified. Categorical variables will be summarized as number and percentage of subjects.

Listings will include all subjects, unless specified otherwise, and will be presented by sequence, treatment and subject.

